6.2. KEY DEFINITIONS

The last non-missing value prior to the start of infusion of any study drug in Period 1 will be used as baseline.

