- Part A - Treatment period 1 - Cohort 3 (0.05 mg/kg SEL-110 + 0.2 mg/kg SEL-037), Cohort 4 (0.05 mg/kg SEL-110 + 0.4 mg/kg SEL-037), Cohort 5 (0.08 mg/kg SEL-110 + 0.2 mg/kg SEL-037), Cohort 6 (0.08 mg/kg SEL-110 + 0.4 mg/kg SEL-037), Cohort 7 (0.1 mg/kg SEL-110 + 0.2 mg/kg SEL-037), Cohort 8 (0.1 mg/kg SEL-110 + 0.4 mg/kg SEL-037), Cohort 10 (0.125 mg/kg SEL-110 + 0.4 mg/kg SEL-037), Cohort 11 (0.15 mg/kg SEL-110 + 0.2 mg/kg SEL-037), and Cohort 12 (0.15 mg/kg SEL-110 + 0.4 mg/kg SEL-037)

- Vitals at the Screening Visit, (Day 0) predose (T-0), intradose (after the start of study drug IV syringe infusion SEL-110) 15, 30, 45, 60, 90, 120 and 180 minutes, then at 6, 9 hours; and then at Day 1, 7, 14, 21 and early termination.
- ECG exam at the Screening Visit, (Day 0) predose, 6 hours after completion of dosing and early termination.
- Part A - Treatment period 2 - Cohort 1 (0.2 mg/kg SEL-037 alone) and Cohort 2 (0.4 mg/kg SEL-037 alone)
 - Vitals at (Treatment Period 2, Day 0) predose (T-0), intradose after the start of study drug IV syringe infusion (saline placebo) at 30, 60, 90, 120 and 180 minutes, then at 6, 9 hours; and then at Treatment Period 2, Day 1, 7, 14, 21 and early termination.
 - ECG exam at (Treatment Period 2, Day 0) predose and early termination.
- Part A - Treatment period 2 - Cohort 3 (0.05 mg/kg SEL-110 + 0.2 mg/kg SEL-037), Cohort 4 (0.05 mg/kg SEL-110 + 0.4 mg/kg SEL-037), Cohort 5 (0.08 mg/kg SEL-110 + 0.2 mg/kg SEL-037), Cohort 6 (0.08 mg/kg SEL-110 + 0.4 mg/kg SEL-037), Cohort 7 (0.1 mg/kg SEL-110 + 0.2 mg/kg SEL-037), Cohort 8 (0.1 mg/kg SEL-110 + 0.4 mg/kg SEL-037), Cohort 10 (0.125 mg/kg SEL-110 + 0.4 mg/kg SEL-037), Cohort 11 (0.15 mg/kg SEL-110 + 0.2 mg/kg SEL-037), and Cohort 12 (0.15 mg/kg SEL-110 + 0.4 mg/kg SEL-037)
 - Vitals at (Treatment Period 2, Day 0) predose (T-0), intradose after the start of study drug IV syringe infusion (SEL-110) at 15, 30, 45, 60, 90, 120, 180 minutes, then at 6, 9 hours; and then at Treatment Period 2, Day 1, 7, 14, 21 and early termination.
 - ECG exam at (Treatment Period 2, Day 0) predose and early termination.
- Part A - Treatment period 3 - Cohort 1 (0.2 mg/kg SEL-037 alone) and Cohort 2 (0.4 mg/kg SEL-037 alone)
 - Vitals at (Treatment Period 3, Day 0) predose (T-0), intradose after the start of study drug IV syringe infusion (saline placebo) at 30, 60, 90, 120, 180 minutes, then at 6, 9 hours; and then at Treatment Period 3, Day 1, 7, 14, 21 and early termination.

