 - Vitals at (Treatment Period 5, Day 0) predose (T-0), intradose after the start of study drug IV infusion (SEL-037) at 15, 30, 45, 60, 90, 120, and 180 minutes, then at 6 hours; and then at Treatment Period 5, Day 1, 7, 14, 21 and 30 or early termination
 - ECG exam at (Treatment Period 5, Day 0) predose and End of Study Treatment Period 5, Day 30 or early termination.
- Part B - Treatment period 5 - Cohort 3 (0.05 mg/kg SEL-110 + 0.2 mg/kg SEL-037), Cohort 4 (0.05 mg/kg SEL-110 + 0.4 mg/kg SEL-037), Cohort 5 (0.08 mg/kg SEL-110 + 0.2 mg/kg SEL-037), Cohort 6 (0.08 mg/kg SEL-110 + 0.4 mg/kg SEL-037), Cohort 7 (0.1 mg/kg SEL-110 + 0.2 mg/kg SEL-037), Cohort 8 (0.1 mg/kg SEL-110 + 0.4 mg/kg SEL-037), Cohort 10 (0.125 mg/kg SEL-110 + 0.4 mg/kg SEL-037), Cohort 11 (0.15 mg/kg SEL-110 + 0.2 mg/kg SEL-037), and Cohort 12 (0.15 mg/kg SEL-110 + 0.4 mg/kg SEL-037)

- Vitals at (Treatment Period 5, Day 0) predose (T-0), intradose after the start of study drug IV infusion (SEL-037) at 15, 30, 45, 60, 90, 120 and 180 minutes, then at 6 hours; and then at Day 1, 7, 14, 21 and 30 or early termination.
- ECG exam at (Treatment Period 5, Day 0) predose and End of Study Treatment Period 5, Day 30 or early termination.
- Adverse events (AE) and serious adverse events (SAE) starting at dosing. AEs will be graded according to Rheumatology Common Toxicity Criteria, version 2.0. If a severe infusion reaction occurs, a determination of anaphylaxis (Grade 4 reaction) will be based on the National Institute of Allergy and Infectious Diseases (NIAID)/ Food Allergy & Anaphylaxis Network (FAAN) Anaphylaxis Criteria.
- Concomitant medication usage will be recorded throughout the trial.
- Clinical laboratory tests (blood chemistry, hematology including clotting parameters, and urinalysis) per the Time and Events Schedule.
- Immunogenicity samples for anti-PEG antibodies at the Screening Visit and for anti-pegsiticase, anti-uricase, and anti-PEG antibodies at baseline (predose for Treatment Periods 1, 2, 3, 4 and 5), Day 7, 14, and 21 post each treatment for Treatment Periods 1, 2, 3, 4, and 5, and EOS / early termination (Treatment Period 5, Day 30).

Safety (Part C, Cohorts 13, 15, and 17):

Note: Cohorts 14 and 16 are intentionally omitted from this protocol in order to maintain the cohort numbering convention of associating odd numbered cohorts with the 0.2 mg/kg SEL-037 dose.

- Physical exam at the Screening Visit and Treatment Period 5, Day 30/early termination.

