12.8. Safety Analyses

Includes subjects in the safety analysis population. Baseline for all laboratory evaluations, vital signs, and ECG measurements will be defined as the last evaluation done before study drug administration.

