19.2. NIAID/FAAN Clinical Criteria for Anaphylaxis

From the Second Symposium on the Definition and Management of Anaphylaxis (Sampson, 2006).

*Anaphylaxis is highly likely when any **one** of the following 3 criteria are present*

1. Acute onset of an illness (minutes to several hours) with involvement of the skin, mucosal tissue, or both (e.g., generalized hives, pruritus or flushing, swollen lips-tongue-uvula)
AND AT LEAST ONE OF THE FOLLOWING
 - a. Respiratory compromise (e.g., dyspnea, wheeze-bronchospasm, stridor, reduced peak expiratory flow, hypoxemia)
 - b. Reduced blood pressure or associated symptoms of end-organ dysfunction (e.g., hypotonia [collapse], syncope, incontinence)

2. Two or more of the following that occur rapidly after exposure to a *likely allergen for that patient* (minutes to several hours):
 - a. Involvement of the skin-mucosal tissue (e.g., generalized hives, itch-flush, swollen lips-tongue-uvula)
 - b. Respiratory compromise (e.g., dyspnea, wheeze-bronchospasm, stridor, reduced peak expiratory flow, hypoxemia)
 - c. Reduced blood pressure or associated symptoms (e.g., hypotonia [collapse], syncope, incontinence)
 - d. Persistent gastrointestinal symptoms (e.g., crampy abdominal pain, vomiting)

3. Reduced blood pressure after exposure to *known allergen for that patient* (minutes to several hours):
 - a. Infants and children: low systolic blood pressure (age specific) or greater than 30% decrease in systolic blood pressure
 - b. Adults: systolic blood pressure of less than 90 mm Hg or greater than 30% decrease from that person's baseline

***Note:** Item 1 will generally apply to subjects in this study since SEL-037 will not be a known or a likely antigen for these subjects.

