11.5. VITAL SIGNS

Pulse, temperature, respiration rate, and systolic and diastolic blood pressure will be analyzed. Data will be flagged according to the reference limits (High or Low), if applicable. Descriptive statistics on actual values and changes from baseline by dose will be computed at each scheduled time point. Plots (mean \pm standard error of the mean [SEM]) on changes from baseline over time will be given as appropriate.

Vital sign data will also be listed.

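### Vital-sign change from baseline is defined only against the Period 1 pre-dose value, so planned dosing-day changes in Periods 2–5 mix the infusion effect with 4 to 16 weeks of drift

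*SAP*

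**What the plan says.** SAP 6.2 gives the general definition: "The last non-missing value prior to the start of infusion of any study drug in Period 1 will be used as baseline". SAP 11.5 states no other baseline for vital signs. It plans: "Descriptive statistics on actual values and changes from baseline by dose will be computed at each scheduled time point". It adds mean ± SEM plots of change over time, as appropriate. The same section says "Data will be flagged according to the reference limits (High or Low), if applicable" and "Vital sign data will also be listed". By SAP 6.1, continuous summaries carry n, mean, SD, median, minimum and maximum, and safety tables use scheduled assessments only.

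Protocol 12.8 words the baseline differently: "Baseline for all laboratory evaluations, vital signs, and ECG measurements will be defined as the last evaluation done before study drug administration". It names no period. SAP 13 declares no departure from the protocol's planned analysis.

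The Protocol Synopsis schedules dosing-day vital signs in every treatment period. In Part A, Periods 2 and 3, the SEL-212 cohorts are measured "intradose after the start of study drug IV syringe infusion (SEL-110) at 15, 30, 45, 60, 90, 120, 180 minutes" and then at 6 and 9 hours; Cohorts 1 and 2 start at 30 minutes. A reading before infusion is also scheduled each time. The Period 5 entry, for instance, opens "Vitals at (Treatment Period 5, Day 0) predose (T-0".

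**The concern.** Dosing-day readings are closely spaced around the infusion, and their natural use is to show what that infusion did. The comparator for an acute effect is the reading taken just before it. The plan uses that comparator in Period 1 only. From Period 2 on, the planned change is measured against a visit weeks earlier.

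This falls in the periods where the protocol itself places more concern: section 4.4.1 says infusion reactions appear more prevalent with multiple dosing, and section 4.5 cites the risk with repeat dosing. Safety is the primary objective. Other planned output does not fill the gap. Laboratory data get pre/post cross-tabulations (SAP 11.4) and QTc gets threshold and change-category listings (SAP 11.6), but vital signs get no count of subjects with a fall. The primary endpoints in SAP 4.3 name ECG and laboratory abnormalities, not vital-sign abnormalities.

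**Working it through.** The plan states no figure on this point, so there is none to reproduce.

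**1. Age of the reference.** Protocol 6.3.1 gives a typical treatment period of 28 days; the Schedule of Events allows ±1 day on dosing visits. Age at the Period p infusion = 28 × (p − 1) days.

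| Period | Nominal age | Range if ±1 day accumulates |
|---|---|---|
| 2 | 28 days (4 weeks) | 27–29 |
| 3 | 56 days (8 weeks) | 54–58 |
| 4 | 84 days (12 weeks) | 81–87 |
| 5 | 112 days (16 weeks) | 108–116 |

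Calendar check: Period 5 Day 30 is 112 + 30 = 142 and the Day 60 visit is 112 + 60 = 172; SAP 6.1 gives 140 and about 170. If the Period 1 predose value is missing, the last non-missing value may be from screening, up to 45 days earlier: 112 + 45 = 157 days.

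**2. What the planned change contains.** Let B be the Period 1 value, T the same-day T-0 and Y an intradose reading. Then Y − B = (Y − T) + (T − B). The first term is the change since that day's T-0. The second is everything that happened between visits.

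**3. Illustration (assumed values).** Take a true same-day systolic fall of 20 mm Hg in Period 5.
- T is 15 above B: planned change = 15 − 20 = −5.
- T is 15 below B: planned change = −15 − 20 = −35.

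**4. Spread (assumed values).** With SD 15 mm Hg at each reading and correlation r, SD of change = 15 × √(2(1 − r)).
- Against Period 1, r from 0.7 to 0.4: 11.6 to 16.4.
- Against same-day T-0, r from 0.9 to 0.8: 6.7 to 9.5.

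The variance ratio is (1 − r between visits)/(1 − r within day). It runs from 0.3/0.2 = 1.5 to 0.6/0.1 = 6.

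**5. What the actual-value tables recover.** T-0 and intradose means for the same period both appear. If the same subjects contribute to both, their difference is the mean same-day change. The SD of that change cannot be recovered, because it needs the within-subject correlation. Nor can the largest individual fall, because a difference of minima is not the minimum of differences. Constructed example: B = 120, T = 150, Y = 100. The same-day fall is 50/150 = 33%; the planned change is −20, which is −17% of 120. The actual value of 100 does not itself show the size of the fall.

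**6. The two baseline texts.** Protocol 12.8 can be read as the last value before the first dose, which agrees with SAP 6.2, or before each administration, which does not. SAP 13 does not settle it.

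**The case against.** A single pre-treatment baseline is a legitimate choice and shows cumulative change over the study. Actual values are summarised at each scheduled time with minimum and maximum, flagged against limits that do not depend on baseline, and listed. Infusion reactions are captured elsewhere: nine hours of observation (Protocol 8.2.2), clinically significant vital-sign abnormalities reported as adverse events (11.2.2.6), graded events, and narratives. SEL-212 cohorts are redosed only if Day 21 uric acid is at or below 1.0 mg/dL (6.3.1), so many subjects losing response leave before the next infusion. All of this stands. It answers the claim that falls would be invisible, but supplies no same-day change.

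Four stronger readings are tempting and unsupported:

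- **That vital signs are analysed only as change from Period 1**, so that haemodynamic safety of doses 2 to 5 cannot be read at all. SAP 11.5 also summarises, flags and lists actual values.
- **That a stated share of large falls would be missed.** Any such rate needs an assumed mean, SD and correlation, and would describe a classification the SAP does not make.
- **That the blood-pressure limits in Protocol 19.2, "systolic blood pressure of less than 90 mm Hg or greater than 30% decrease from that person's baseline", are the study's working criterion for anaphylaxis.** They belong to Item 3, for a known allergen. The protocol's note says Item 1 generally applies, and the quoted words do not say same-day.
- **That the SAP contradicts the protocol.** Protocol 12.8 is ambiguous rather than opposed. Likewise, that the vital-sign schedule exists to catch infusion reactions is a fair inference from Protocol 8.2.2, not a stated purpose.

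**Conclusion.** The point holds as a gap in the analysis definition. For Periods 2 to 5, every planned dosing-day change in vital signs refers to a reading nominally 4, 8, 12 or 16 weeks old, while the better reference for an acute effect is scheduled and unused. The ages follow from the protocol's 28-day period. The size of the distortion cannot be derived from the documents, which give no blood-pressure variability; the −5 and −35 figures and the variance ratios of 1.5 to 6 are illustrations under the assumptions stated.

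The consequence is limited. A mean same-day change can be approximated from the actual-value tables, and individual falls can be worked out from listings. Its spread and the number of subjects with a same-day fall are not planned output. This is an inexpensive improvement to a descriptive safety analysis and does not invalidate it.

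**What to change.** In SAP 6.2 and 11.5:

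- For vital signs on Day 0 of each treatment period, compute change for readings after T-0 from that period's own T-0, defined as the last reading before that day's first infusion starts. State that an earlier value is not substituted if T-0 is missing.
- Keep the Period 1 baseline for longer-term change: each period's predose value, Days 1, 7, 14 and 21, and End of Study.
- Reconcile SAP 6.2 with Protocol 12.8 so that both name the period, and amend SAP 13 if the agreed reading departs from the protocol.

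Optionally, add a table by cohort and treatment period of n (%) of infused subjects with systolic pressure below 90 mm Hg or a fall of more than 30% from same-day T-0. Label it descriptive and not a diagnosis of anaphylaxis, since the limits come from Item 3 of Protocol 19.2.

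The cost is SAP wording, some extra tables and plots, and two baselines that must be clearly labelled. All values are already scheduled, no procedure changes, and nothing is lost because the Period 1 change is retained.

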6.3. MISSING DATA

The handling of missing PK data is detailed in SAP section 8.2.1.

The handling of missing PD data is detailed in SAP section 9.3.1.

Statistical Analysis Plan

7. DEMOGRAPHIC, OTHER BASELINE CHARACTERISTICS AND MEDICATION

7.1. SUBJECT DISPOSITION AND WITHDRAWALS

Subject disposition will be listed. Summary tables reflecting the number of subjects for the following will be presented:

- Screened subjects
- Randomized subjects
- Safety analysis set
- PK analysis set
- PD analysis set
- Subjects who complete the study
- Subjects who early terminate the study and reasons for early termination

Screen Failure subjects will be listed.

7.2. DEMOGRAPHIC AND OTHER BASELINE CHARACTERISTICS

Demographic characteristics such as sex, age, race, and ethnicity will be summarized for Safety Analysis Set, by treatment and overall. Demographic characteristics will be also listed for Safety Analysis Set.

7.3. MEDICAL HISTORY AND CONCOMITANT DISEASES

Medical history will be listed by treatment and subject. Summaries will be provided. Medical history will be coded by using the most recent (MedDRA®) version.

7.4. MEDICATION

Concomitant therapy includes any medication (eg, prescription drugs, over-the-counter drugs, vaccines, topical medications, herbal or homeopathic remedies, nutritional supplements) used by a subject from 3 months prior to screening to the last study visit. All such medications should be reported to the investigator and recorded on the Concomitant Medications electronic case report form (eCRF). The reported medications will be reviewed and evaluated by the investigator or designee to determine if they affect a subject's eligibility to participate or continue to participate in the study.

1008142

SELECTA Biosciences

SEL - 212/201

SAP Version: Final 2.0

Statistical Analysis Plan

The original verbatim terms collected in the eCRF for concomitant medications will be coded using the World Health Organization Drug Dictionary (WHO-DD September 2015 version) into drug class (Anatomical Therapeutic Classification [ATC] level 4) and preferred term.

Concomitant medication will be listed and summarized.

Statistical Analysis Plan

8. ANALYSIS OF PHARMACOKINETICS

The PK analysis set will be used to calculate PK parameters, graphical displays of individual data, and the listings of PK concentrations and parameters, and for all PK summaries. Subjects with missing PK parameters due to unreliable or missing data will be flagged and excluded from summarization.

Concentrations of pegsiticase and uricase activity in serum at different time points will be used as measures of the PK of SEL-037. Concentrations of rapamycin in whole blood will be used to characterize the PK of SEL-110.

The Parts A/B (Treatment periods 1-3 and 4-5 for cohorts 1-8, 10-12 respectively) will be presented together, Part C (cohorts 13 and 15) will be presented separately unless necessary for comparative analysis.

Statistical Analysis Plan

8.1. COLLECTION SCHEDULE

Cohorts 1-2

Period	Day	Time from start of dose for saline, h	Time from start of dose for SEL-037, h	
			SEL-037 PK concentration	Uricase activity
1-3	0	0	-1 (0)	-1 (0)
		1.5		0.5
		2		1
		3		2
		6		5
		9		8
		1	23	23
		7	167	167
		14	336	335
	21	504	503	
	28*	672	671	
4-5	0		0	0
			0.5	0.5
			1	1
			1.5	1.5
			2	2
			3	3
			6	6
		1	24	24
		7	168	168
		14	336	336
	21	504	504	
28**	672	672		
30***		720	720	

* - pre-dose for next Treatment period

** - PK point for Treatment period 4 as pre-dose for Treatment period 5

*** - last point for Treatment period 5 only

Repeat the same for other periods

Statistical Analysis Plan

Cohorts 3-8, 10, 11, 12

Period	Day	Time from start of dose for SEL-110, h	Time from start of dose for SEL-037, h	
		SEL-110 concentration	SEL-037 PK concentration	Uricase activity
1-3	0	0	-1 (0)	-1 (0)
		0.25		
		0.5		
		0.75		
		1.5	0.5	
		2	1	
		3	2	
		6	5	
		9	8	
	1	23	23	
	7	167	167	
	14	336	335	
	21	504	503	
	28*	672	671	
4-5	0		0	
			0.5	
			1	
			1.5	
			2	
			3	
	1	6	24	24
	7	168	168	168
	14	336	336	336
	21	504	504	504
28**	672	672	672	
30***	720	720	720	

* - pre-dose for next Treatment period

** - PK point for Treatment period 4 as pre-dose for Treatment period 5

*** - last point for Treatment period 5 only

Statistical Analysis Plan

Cohorts 13, 15, 17

Period	Day	Time from start of dose for SEL-110, h	Time from start of dose for SEL-037, h	
		SEL-110 concentration	SEL-037 PK concentration	Uricase activity
1-5	0	0	-1 (0)	-1 (0)
		0.25		
		0.5		
		0.75		
		1.5	0.5	
		2	1	
		3	2	
		6	5	
		9	8	
		1	23	23
		7	167	167
14	336	335		
21	504	503		
28*	672	671		
30**		720		

* - pre-dose for next Treatment period

** - last point for Treatment period 5 only

8.2. PHARMACOKINETIC PARAMETERS

The following PK parameters will be calculated on SEL-037 and SEL-110 (rapamycin) PK concentration as well as uricase activity using noncompartmental intravascular infusion log-linear model for each Cohort and Treatment Period where possible and summarized statistically:

C_{max}	Maximum observed PK concentration or activity
T_{max}	Time of maximum observed PK concentration or activity
C_{last}	Last observed PK concentration or activity
T_{last}	Time of last observed PK concentration or activity
AUC_{0-last}	Area under the serum concentration-time curve from time zero to the time of the last quantifiable PK concentration or activity
AUC_{0-inf}	Area under the PK concentration or activity-time curve from time zero extrapolated to infinity
$t_{1/2}$	Terminal elimination half-life
λ_z	Terminal elimination rate constant
CL	Clearance of drug
V_d	Terminal volume of distribution

Statistical Analysis Plan

Additional PK parameters may be calculated as needed.

Multiple dose parameters will be also derived where possible:

C_{min}	Min observed trough PK concentration or activity
T_{min}	Time of min observed PK concentration or activity
C_{ave}	Average observed PK concentration or activity
AUC_{tau}	Area under the PK concentration or activity from time 0 to the end of dosing interval
% Fluctuation	Difference between C_{max} and C_{min} normalized by average concentration
R_{AUCtau}	Accumulation ratio based on comparison of AUC_{tau} between last and first dose
R_{Cmax}	Accumulation ratio based on comparison of C_{max} between last and first dose
R_{Cmin}	Accumulation ratio based on comparison of C_{min} between last and first dose
CL_{ss}	Steady state clearance (if steady state is achieved)

Dose dependent parameters for SEL-110 (C_{max} , AUC_{0-last} , AUC_{0-inf}) will be dose normalized for comparison between treatments involving different doses of SEL-037.

The PK parameters will be estimated as follows:

The apparent C_{max} and the corresponding T_{max} will be read directly from the concentration-time plot (observed data, not predicted data by the program);

AUCs will be calculated using the linear-log trapezoidal rule;

The terminal elimination rate constant (λ_z) will be determined by log linear regression obtained on at least the 3 last quantifiable concentrations and will not include C_{max} . The adjusted square of the correlation coefficient (Rsquare adjusted) for the goodness of fit of the regression line through the data points must be at least 0.8500 for the λ_z value to be considered reliable;

$t_{1/2}$ is calculated by the program as $\ln 2 / \lambda_z$;

If the time interval between the lower and upper time points used for the regression spans less than the derived half-life itself then λ_z and the associated $t_{1/2}$ will be considered unreliable;

The AUC from 0 to infinity is calculated by the program as:

$AUC_{inf} = AUC_{last} + AUC_{last-inf}$ where last is the sampling time point of the last measurable concentration (t_{last}). $AUC_{last-inf}$ is calculated by the program as: C_{last} / λ_z , where C_{last} is the

Statistical Analysis Plan

observed concentration at time t_{last} and λ_z is the elimination rate constant during the apparent terminal elimination phase; AUC_{inf} will only be presented for subjects with a reliable λ_z ;

The AUC extrapolation to infinity must be $\leq 20\%$ of the total area for AUC_{inf} to be considered reliable;

CL is calculated by program as $(dose/AUC_{inf})$

V_d is calculated by the program as $(dose/AUC_{inf})/\lambda_z$.

For subjects with unreliable λ_z (ie, Rsquare adjusted < 0.8500 , interval for λ_z calculation shorter than $t_{1/2}$, number of points to calculate $\lambda_z < 3$), λ_z , $t_{1/2}$, AUC_{inf} , CL and V_d will be flagged in the individual data.

For subjects with unreliable AUC_{inf} (because of extrapolation $> 20\%$), AUC_{inf} , CL and V_d will be flagged in the individual data.

Flagged PK parameters will be excluded from summarization and statistical analyses.

8.2.1. Handling of Dropouts, Missing Data or Data Below the Lower Limit of Quantification

Missing concentration data for all subjects who are administered scheduled study treatments will be considered as non-informative missing and will not be imputed for each treatment period individually. The missing data will not affect analyses for the previous treatment periods where complete dose were administered and PK profiles available. No concentration estimates will be provided for missing sample values.

For the derivation of PK parameters, the following rules will apply:

Concentration values below the assay's lower limit of quantification (BLQ) in pre-dose samples and in samples taken before the time of the first quantifiable concentration will be treated as zero.

The sampling time of pre-dose samples relative to dosing will also be treated as zero.

Post-dose BLQ values after the first quantifiable time point will be set to missing.

If the actual time of sampling is missing, the planned time may be used.

Statistical Analysis Plan

Samples taken outside the sampling windows may be excluded from by-time point summary statistics. This will be determined prior start of analyses around timing for database lock.

For serum or whole blood concentration summary, individual concentration versus time curves and mean concentration versus time graphs, the following rules will apply:

- Serum or whole blood concentrations BLQ in pre-dose samples and in samples taken before the time of the first quantifiable value will be set to zero
- The serum or whole blood concentrations BLQ after quantifiable concentration will be set to zero

No further imputation will be applied to any missing values.

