4.5.1. Rationale for Dose Selected (Part C)

Dosing in the Part C of this Phase II study (SEL-212/201) of up to 0.15 mg/kg SEL-110 in combination with 0.2 mg/kg SEL-037 (ie, SEL-212) is similarly supported by the nonclinical and clinical data presented in Section 4.3.1 and Section 4.3.2, respectively. From our review of interim serum uric acid and antibody data from Part A and B cohorts, we believe that 5 doses of the combination may be allow enhanced reduction of antibodies and serum uric acid for the duration of the therapy. Similar to Parts A & B, doses of 0.2 mg/kg SEL-037 were selected for Part C based on preclinical evaluation in rodent, rat, and monkey (Section 4.3.1.1) and clinical evaluation in two completed Phase I studies. Support for 3 doses of SEL-110 in combination with SEL-037 is described above for Part A and B. We have continued to extend our toxicology program to include additional doses of SEL-110 alone and in combination with SEL-037. We will submit toxicology data that demonstrates the safety of delivering 5 doses at up to 0.15 mg/kg SEL-110 prior to any patients receiving the 4th dose of SEL-212 in Part C. Should a delay occur such that the toxicology data to support the safety of the 4th and 5th doses of the combination of SEL-212 at the proposed doses is not available at the scheduled time of the 4th dose for a subject, that subject will be converted from the planned regimen of 5 doses of SEL-212 to a receive only SEL-037 at 0.2 mg/kg at the 4th and 5th dose and hence converted to a regimen of 3 doses of SEL-212 followed by 2 doses of SEL-037. This regimen is similar to the regimen of previous cohorts in Part A and B.

To investigate dose ranging in the 5 combination dosing regimen, Cohort 17 will have 5 doses of SEL-110 at a lower dose of 0.1 mg/kg at all 5 treatment periods and Cohort 15 will have 4 doses of SEL-110 at a lower dose of 0.1 mg/kg at treatment periods 2-5. Preliminary analyses of data in the Phase I study (SEL-212/101) and cohorts in Part A and Part B suggest that the first treatment period may be a critical time period for preventing antibody development to SEL-037; thus increased doses of SEL-110 in the first treatment period may help achieve a higher rate of patients who do not develop antibodies to SEL-037. As such, the first dose of SEL-110 in

treatment period 1 will be at a higher dose of 0.15 mg/kg in Cohort 15 to allow for comparison of efficacy and safety with other regimens in Part C.

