In Part A and Part B, approximately 100 subjects will be divided into 11 dosing cohorts, each consisting of 6-20 subjects. Cohort 1 will receive SEL-037 (pegsitacase alone, 0.2 mg/kg). Cohort 2 will receive SEL-037 (pegsitacase alone, 0.4 mg/kg), Cohort 3 will receive SEL-212 (with 0.05 mg/kg of SEL-110 + 0.2 mg/kg pegsitacase), Cohort 4 will receive SEL-212 (with 0.05 mg/kg of SEL-110 + 0.4 mg/kg pegsitacase), Cohort 5 will receive SEL-212 (with 0.08 mg/kg of SEL-110 + 0.2 mg/kg pegsitacase), Cohort 6 will receive SEL-212 (with 0.08 mg/kg of SEL-110 + 0.4 mg/kg pegsitacase), Cohort 7 will receive SEL-212 (with 0.1 mg/kg of SEL-110 + 0.2 mg/kg pegsitacase) and Cohort 8 will receive SEL-212 (with 0.1 mg/kg of SEL-110 + 0.4 mg/kg pegsitacase), Cohort 10 will receive SEL-212 (with 0.125 mg/kg of SEL-110 + 0.4 mg/kg pegsitacase), Cohort 11 will receive SEL-212 (with 0.15 mg/kg of SEL-110 + 0.2 mg/kg pegsitacase), and Cohort 12 will receive SEL-212 (with 0.15 mg/kg of SEL-110 + 0.4 mg/kg pegsitacase). Note that Cohort 9 is intentionally omitted in order to maintain the cohort numbering convention of associating even numbered cohorts with the 0.4 mg/kg SEL-037 dose.

In Part C, up to 40 patients naïve to SEL-212 will be enrolled. Patients enrolled in Cohort 13 will receive SEL-212 (0.15 mg/kg SEL-110 + 0.2 mg/kg SEL-037). Patients enrolled in Cohort 15 will receive an initial induction dose of SEL-212 (0.15 mg/kg SEL-110 + 0.2 mg/kg SEL-037) and, then, four subsequent doses of SEL-212 (0.10 mg/kg SEL-110 + 0.2 mg/kg SEL-037). Patients enrolled in Cohort 17 will receive SEL-212 (0.10 mg/kg SEL-110 + 0.2 mg/kg SEL-037). (Note: Cohort 14 and 16 are intentionally omitted in order to maintain the cohort numbering convention of associating odd numbered cohorts with the 0.2 mg/kg SEL-037 dose.) Subjects who withdraw early, or have significant protocol violations or compliance issues may be replaced at the discretion of the Sponsor to assure completion of the objectives of the clinical study and to maintain the integrity of the data set.

Statistical Analysis Plan

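### The SEL-110 accumulation ratios are not dose-normalised, so Cohort 15, which steps from 0.15 to 0.10 mg/kg after the first dose, gets ratios low by a factor of up to about 1.5 that cannot be compared with Cohorts 13 and 17

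*SAP*

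**What the plan says.** SAP 8.2, repeating the list in 4.1, defines three accumulation ratios: R_AUCtau as "Accumulation ratio based on comparison of AUC_{tau} between last and first dose", R_Cmax as "Accumulation ratio based on comparison of C_{max} between last and first dose" and R_Cmin as "Accumulation ratio based on comparison of C_{min} between last and first dose". None has a dose term. The section covers SEL-110 (rapamycin), SEL-037 and uricase activity, with parameters derived "for each Cohort and Treatment Period where possible and summarized statistically".

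The one sentence on dose normalisation for SEL-110 names Cmax, AUC0-last and AUC0-inf, which "will be dose normalized for comparison between treatments involving different doses of SEL-037". AUCtau and Cmin are not named, and comparisons between periods within a cohort are not mentioned.

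SAP 3.7 gives Cohort 15 an induction dose containing 0.15 mg/kg SEL-110. Protocol 4.5.1 says that "Cohort 15 will have 4 doses of SEL-110 at a lower dose of 0.1 mg/kg at treatment periods 2-5". SEL-037 stays at 0.2 mg/kg throughout. SEL-110 is sampled in all five Part C periods (SAP 8.1; protocol Table 11), and no exception is made for Cohort 15.

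**The concern.** An accumulation ratio is meant to show how exposure builds up when the same dose is repeated. In Cohort 15 the numerator comes from a dose one third smaller than the dose behind the denominator, so the ratio mixes any accumulation with a planned dose reduction.

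Rapamycin PK after multiple infusions is a secondary objective, and Part C extends SEL-110 from three combination doses to five. Protocol 4.5.1 includes Cohort 15 so that it can be compared with the other Part C regimens. Cohorts 13 and 17 keep a constant SEL-110 dose, so their ratios mean what the label says. Tabulated beside them, the Cohort 15 ratio would suggest different kinetics where only the dose differs.

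**Working it through.** Neither document states an expected accumulation ratio, so there is no figure to reproduce.

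**Inputs**
- Cohort 15 SEL-110 doses: 0.15, then 0.10 four times (SAP 3.7). There is no maximum dose at or above 0.10 mg/kg (protocol 9.4.2), so the ratio in mg is also about 1.5, apart from weight change.
- Dosing interval: 28 days = 672 h (protocol 6.3.1).
- Phase 1 mean half-lives: 207.6 to 299.7 h across cohorts; 284.4 h for 0.3 mg/kg SEL-110 + SEL-037. Individual values run from 25 to 375 h (protocol Table 7).
- Phase 1 mean AUC0-last, AUC0-inf and Cmax: protocol Table 7.

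**1. No accumulation, dose-proportional exposure.** Ratio = 0.10/0.15 = 0.667.

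**2. AUC, using Table 7.** With linear kinetics and a constant dose, R_AUCtau tends to AUC0-inf/AUCtau. If Phase 1 AUC0-last stands in for AUCtau (the last Phase 1 sampling time is not given), the two cohorts with the same N for both parameters give:
- 0.3 mg/kg + SEL-037 (N=5): 37950.3/37015.0 = 1.025; un-normalised Cohort 15 ratio 1.025/1.5 = 0.683.
- 0.5 mg/kg alone (N=4): 39812.8/37537.9 = 1.061; un-normalised ratio 1.061/1.5 = 0.707.

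**3. Mono-exponential scenario.** Let x = 2^(-672/t½). For five equal doses, R = 1 + x + x² + x³ + x⁴. Cohort 15 as the SAP defines it: [0.10(1 + x + x² + x³) + 0.15x⁴]/0.15.

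| t½ (h) | equal doses | Cohort 15 as planned |
|---|---|---|
| 207.6 | 1.119 | 0.746 |
| 284.4 | 1.241 | 0.828 |
| 299.7 | 1.267 | 0.846 |

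The shortfall factor at dose 5 is 1.496 to 1.500 for half-lives up to 375 h.

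**4. Does the mono-exponential model fit Table 7?** It implies AUC = Cmax × t½/ln 2. For 0.3 mg/kg + SEL-037: 2434.4 × 284.4/0.693 ≈ 999,000 h*ng/mL, against 37,950 reported, about 26 times too large. Most exposure therefore precedes the terminal phase. The model overstates AUC and Cmax accumulation. It suits troughs better, because they lie in the terminal phase.

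**5. Earlier last dose.** If dose 2 is the last, the shortfall factor is 1.5(1 + x)/(1 + 1.5x): 1.43 at 208 h, 1.39 at 284.4 h and 1.35 at 375 h. If dose 3 is the last, it is 1.46 to 1.49.

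**6. Effect of dividing by dose (284.4 h, mono-exponential).** The planned ratio is multiplied by 1.5.
- Dose 5: 0.828 becomes 1.242 (equal-dose value 1.241).
- Dose 3: 0.834 becomes 1.251 (1.232).
- Dose 2: 0.861 becomes 1.292 (1.194), slightly high because of carry-over from the 0.15 mg/kg dose.

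**7. Sensitivity to proportionality.** Protocol 4.3.2.3 reports a slope of about 1.2 for SEL-110 with SEL-037. The dose step would then be worth 1.5^1.2 = 1.63, and dividing by dose would leave a residual of 1.63/1.5 ≈ 1.08.

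**The case against.** The strongest case against the point concerns its weight. These are three descriptive ratios for one analyte in one of 14 cohorts. No hypothesis test, stopping rule or primary endpoint uses them. Results are shown by cohort, and the Cohort 15 label shows the step-down. The five periods are overlaid on one concentration plot (SAP 8.4). Clearance divides by dose. SAP 8.5 uses SEL-110 dose as a regressor, and SAP 8.2 allows additional parameters. A normalised ratio could be computed at reporting from recorded doses.

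Most of that is fair, and it limits the seriousness. It does not remove the defect. Clearance in later periods is itself affected by carry-over. SAP 8.5 combines only Part C periods 1 to 3 with Part A. A permission to add parameters is not a plan to add this one. SAP 8.6 already dose-normalises Cmin and AUCtau for SEL-037, so the step is familiar to the plan and is missing where the SEL-110 dose changes.

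A reader might also infer that the plan conceals accumulation of 12 to 27%, by setting the mono-exponential 1.12 to 1.27 against 0.75 to 0.85. The documents do not support that for AUC or Cmax. Table 7 contradicts the model by a factor of about 26, and its AUC ratios point to AUC accumulation of only a few percent. Nor is 1.5 uniform. Subjects above 1.0 mg/dL at Day 21 get no further dose (protocol 6.3.1), and protocol 4.5.1 allows doses 4 and 5 to become SEL-037 alone, so the last SEL-110 dose may come earlier.

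**Conclusion.** The point holds for SEL-110 in Cohort 15 only. Followed as written, SAP 4.1 and 8.2 produce ratios low by a factor of up to about 1.5 under dose-proportional exposure, and by about 1.35 to 1.43 under a mono-exponential model if dose 2 is the last. They cannot be read alongside Cohorts 13 and 17. The un-normalised R_AUCtau would be about 0.68 to 0.71 if Phase 1 AUC0-last approximates AUCtau, close to the 0.67 expected from the dose step alone. The range of 0.75 to 0.85 is an upper scenario that matters mainly for R_Cmin. The direction and cause of the error are clear from the text. How much true accumulation it would obscure is uncertain and, for AUC, probably small. This is a correctable error in a descriptive output for a secondary objective and does not threaten the trial's main conclusions.

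**What to change.** In SAP 4.1 and 8.2, state that SEL-110 R_AUCtau, R_Cmax and R_Cmin are calculated from parameters divided by the SEL-110 dose actually given in that period. Actual dose is the right divisor because doses are recalculated from Day 21 weight (protocol 9.4).

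Report the Cohort 15 ratios by number of SEL-110 doses received. Footnote the accumulation-ratio table to say that carry-over from the first dose makes the normalised ratio slightly high when few doses were given.

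Taking Treatment Period 2 as the Cohort 15 reference would not solve the problem. That period carries residue from the 0.15 mg/kg dose, and under the mono-exponential model the ratio [0.10(1 + x + x² + x³) + 0.15x⁴]/(0.10 + 0.15x) is 0.965, 0.961 and 0.963 at 207.6, 284.4 and 299.7 h, still below 1.

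The cost is a sentence in each section, one division in the derivation program, a split of one table and a footnote. No new data and no change to dosing are needed.
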